13. ETHICAL CONSIDERATIONS

13.1. Ethical Standard

The investigator will ensure that this study is conducted in full conformity with the principles set forth in The Belmont Report: Ethical Principles and Guidelines for the Protection of Human Subjects of Research, as drafted by the US National Commission for the Protection of Human Subjects of Biomedical and Behavioral Research (April 18, 1979), the Declaration of Helsinki (2013), the ICH E6, and local regulations.

13.2. Research Ethics Committees (REC)

The protocol, informed consent form(s), recruitment materials, and all subject materials will be submitted to the REC for review and approval. Approval of both the protocol and the consent form must be obtained before any subject is enrolled. Any amendment to the protocol will require review and approval by the REC before the changes are implemented in the study.

13.3. Informed Consent Process

Informed consent is a process that is initiated prior to the individual agreeing to participate in the study and continues throughout study participation. Extensive discussion of risks and possible benefits of study participation will be provided to subjects and their families, if applicable. A consent form describing in detail the study procedures and risks will be given to the subject. Consent forms will be REC-approved, and the subject is required to read and review the document or have the document read to him or her. The investigator or designee will explain the research study to the subject and answer any questions that may arise. The subject will sign the informed consent document prior to any study-related assessments or procedures. Subjects will be given the opportunity to discuss the study with their surrogates or think about it prior to agreeing to participate. They may withdraw consent at any time throughout the course of the study. A copy of the signed informed consent document will be given to subjects for their records. The rights and welfare of the subjects will be protected by emphasizing to them that the quality of their clinical care will not be adversely affected if they decline to participate in this study.

The consent process will be documented in the clinical or research record.

13.4. Subject Confidentiality

Subject confidentiality is strictly held in trust by the participating investigators and their staff. This confidentiality is extended to cover testing of biological samples and genetic tests in addition to the clinical information relating to participating subjects. All patients will be identified by the subject number, initials, date of birth and gender in the CRFs. Subject's name will only be maintained at site. The investigator must assure that subjects' anonymity will be maintained and that their identities are protected from unauthorized parties. The subjects should be informed about the possibility of audits by authorized representatives of the company and regulatory authorities when audit or review is required.

The study protocol, documentation, data, and all other information generated will be held in strict confidence. No information concerning the study or the data will be released to any unauthorized third party without prior written approval of the investigator.

The study monitor or other authorized representatives of the investigator may inspect all documents and records required to be maintained by the investigator, including but not limited to, medical records (office, clinic, or hospital) and pharmacy records for the subjects in this study. The clinical study site will permit access to such records.

13.5. Protocol Amendments

Any change of this protocol that affect study objectives, study design, study procedures, patient population, or significant administrative procedures will require a formal amendment to the protocol. Any proposed protocol amendments must be sent in written form to the REC/TFDA. Prior to implementation, an amendment must be approved by the Sponsor, the Investigator and the REC/TFDA.

14. PUBLICATION POLICY

Following completion of the study, the investigator is expected to publish the results of this research in a scientific journal. Member journals of The International Committee of Medical Journal Editors have adopted a trials-registration policy as a condition for publication. This policy requires that all clinical trials be registered in a public trials registry such as ClinicalTrials.gov, which is sponsored by the National Library of Medicine. Other biomedical journals are considering adopting similar policies. For grants and cooperative agreements, it is the Golden Biotechnology Corporation's responsibility to register the trial in an acceptable registry.

The ICMJE defines a clinical trial as any research project that prospectively assigns human subjects to intervention or comparison groups to study the cause-and-effect relationship between a medical intervention and a health outcome. Studies designed for other purposes, such as to study pharmacokinetics or major toxicity (e.g., Phase I trials), would be exempt from registering trials in a public registry such as ClinicalTrials.gov. The sponsor shall have the right to publish or present any results or information, including the study results. Once if the sponsor or the institution, investigator or the staff intend to publish the study results, mutual agreement shall be obtained at least thirty (30) business days prior to the submission for publication or presentation.

**Protocol: GHLIP-2-001**

**Study Sponsor: Golden Biotechnology Corporation**

## **ABBREVIATIONS**

ABBREVIATIONS	DEFINITION
ABI	Ankle-brachial Index
AE	Adverse Event
ALT	Alanine Aminotransferase
ANCOVA	Analysis of Covariance
AST	Aspartate Aminotransferase
baPWV	Brachial-ankle Pulse Wave Velocity
BMI	Body Mass Index
BUN	Blood Urea Nitrogen
CDMS	Clinical Data Management Systems
CPK	Creatine Phosphokinase
CRF	Case Report Form
CRO	Contract Research Organization
CRP	C-reactive Protein
CV	Cardiovascular
CV(%)	Coefficient of Variation
CVD	Cardiovascular Diseases
DBP	Diastolic Blood Pressure
eGFR	Estimated glomerular filtration rate
GCP	Good Clinical Practice
ECG	Electrocardiogram

**Protocol: GHLIP-2-001**

**Study Sponsor: Golden Biotechnology Corporation**

HDL-C	High-density Lipoprotein Cholesterol
HF	Heart Failure
hsCRP	High Sensitivity assay of C-reactive Protein
HU	Hounsfield Unit
ICH	International Conference on Harmonization
IL-1	Interleukin 1
IL-6	Interleukin 6
ITT	Intent-to-Treat
kg	Kilogram
LDL-C	Low-density Lipoprotein Cholesterol
LDL-R	Low-density Lipoprotein Receptor
m	Meter
m 	Meters Squared
MedDRA	Medical Dictionary for Regulatory Activities
mg	Milligram
PT	Preferred Term
PP	Per-Protocol
RBC	Red blood cell
SAE	Serious Adverse Event
SAS	Statistical Analysis System®
SBP	Systolic Blood Pressure
SD	Standard Deviation
SOC	System Organ Class

**Protocol: GHLIP-2-001**

**Study Sponsor: Golden Biotechnology Corporation**

SOP Standard Operating Procedure

TC Total Cholesterol

TG Triglyceride

WBC White blood cell

---

**Protocol: GHLIP-2-001**

**Study Sponsor: Golden Biotechnology Corporation**

## **1 PREFACE**

Dyslipidemia is a health risk, and epidemiologic studies have shown a link between total cholesterol levels and the risk of cardiovascular diseases (CVD). Previous studies have shown that lowering the levels of total and low-density lipoprotein cholesterol (LDL-C) are associated with decreasing in cardiac morbidity and mortality, whilst epidemiological evidence consistently indicate moderate and highly significant associations between triglyceride (TG) values and coronary heart disease risk. Studies have shown that Antroquinonol® enhances the expression of low-density lipoprotein receptor (LDLR) genes in liver cells responsible for the removal of cholesterol in low-density lipoprotein cholesterol (LDL-C) from the blood stream and significantly increased high-density lipoprotein cholesterol (HDL-C) level ( $p<0.001$ ) in plasma compared to vehicle control. These results demonstrate the potential applications of Antroquinonol® in treating hyperlipidemia and prevent associated CVDs. In this study, Antroquinonol® will be served as the study treatment to assess the reduction of TG in comparison with placebo in patients with hypercholesterolemia and hyperlipidemia after 12 weeks.

## **2 PURPOSE**

The purpose of this SAP is to outline the planned statistical analyses to be completed to support the completion of the Clinical Study Report (CSR) for protocol GHLIP-2-001. The planned analyses identified in this SAP will be included in regulatory submission and/or future manuscripts. Also exploratory analyses not necessarily identified in this SAP may be performed to support the clinical development program. Any post-hoc, or unplanned, analyses not

**Protocol: GHLIP-2-001**

**Study Sponsor: Golden Biotechnology Corporation**

identified in this SAP performed will be clearly identified in the respective CSR.

## **3 STUDY OBJECTIVES AND ENDPOINTS**

### **3.1 Study Objectives**

#### **3.1.1 Primary Objective**

The primary objective is to demonstrate the reduction of TG by Antroquinonol, in comparison with placebo, after 12 weeks of treatment in patients with hypercholesterolemia and hyperlipidemia.

#### **3.1.2 Secondary Objectives**

Secondary objectives include the evaluation of the effects of Antroquinonol in comparison with placebo on other lipid parameters, left ventricular diastolic function, arterial stiffness, and fatty liver after 12 weeks of treatment. The safety and tolerability of Antroquinonol will be monitored as well.

### **3.2 Study Endpoints**

#### **3.2.1 Primary Endpoint**

The primary efficacy endpoint is the percentage change of TG by Antroquinonol, in comparison with placebo, after 12 weeks of treatment in patients with hypercholesterolemia and hyperlipidemia.

**Protocol: GHLIP-2-001**

**Study Sponsor: Golden Biotechnology Corporation**

### **3.2.2 Secondary Endpoints**

1. The effect of Antroquinonol in comparison with placebo on the percentage change in total cholesterol, HDL-C, LDL-C and HDL/LDL ratio from baseline after 12 weeks of treatment.
2. The effect of Antroquinonol on the ratio of mitral velocity to early diastolic velocity of the mitral annulus (E/E' ratio) with tissue Doppler imaging and baPWV and ABI via a non-invasive arterial stiffness measurement.
3. The effect of Antroquinonol on the fatty liver prognostic with CT scan.

### **3.2.3 Safety Endpoints**

1. Changes in laboratory examination including hematological, biochemical parameters, and urinary analysis.
2. Changes in electrocardiogram test, vital signs, and physical examinations.
3. Analysis of adverse events.
4. Compliance and tolerability of the study drug

## **4 STUDY METHOD**

### **4.1 Overall Study Design and Plan**

The study design is constructed as a multi-center, prospective, double-blind, randomized, placebo-controlled study to assess the reduction of TG by Antroquinonol, in comparison with placebo, after 12 weeks of treatment in patients aged between 20 and 75 years with hypercholesterolemia and hyperlipidemia. Enrolled patients are randomized in 1: 1: 1: 1 ratio to Antroquinonol 150 mg, Antroquinonol 100 mg, Antroquinonol 50 mg, or placebo.

Protocol: GHLIP-2-001

Study Sponsor: Golden Biotechnology Corporation

#### 4.1.1 Study Flow Chart

Flow Chart of the Study Schedule

Procedure	Screening *	Randomize	Treatment Period			Follow-up
Visit	Visit 1	Visit 2	Visit 3	Visit 4	Visit 5	Visit 6
Interval	Day -14	Day 1 (Week 1)	Day 29 (Week 5)	Day 57 (Week 9)	Day 85 (Week 13)	Day 99 (Week 15)
Allow Window	-	-	±3	±3	±3	±3
Informed Consent	X					
Assessment of Eligibility Criteria	X					
Medical History	X					
Demographic	X					
Vital Signs 	X	X	X	X	X	X
Anthropometric measures 	X	X	X	X	X	X
Electrocardiogram		X			X	
Physical Examination	X	X	X	X	X	X
Urine Pregnancy Test	X					
Randomization 		X				
Drug Dispense		X	X	X		
Drug Return			X	X	X	
Efficacy Assessment						
Serum Lipid 	X	X	X	X	X	X
baPWV and ABI		X			X	
Image Monitoring 		X			X	
Biomarker Assessment						
CRP and Cytokine 		X			X	X
Safety Assessment						
CBC and WBC differential 		X			X	X
Biochemistry 	X	X	X	X	X	X
Urinary Exam 		X			X	X

**Protocol: GHLIP-2-001**

**Study Sponsor: Golden Biotechnology Corporation**

Concomitant Therapy	X	X	X	X	X	X
Adverse Event		X	X	X	X	X

\* A wash-out period of 2 weeks will not be applied to patients prior treated with medication which does not affect serum lipid level.

1. Vital signs: pulse rate, body temperature, respiratory rate, and blood pressure (including systolic blood pressure (SBP) and diastolic blood pressure (DBP)).
2. Including height, weight, waist circumference, and BMI (calculated by kg/m^2)
3. Subjects who meet the eligibility criteria will be randomized into treatment arms. If the eligibility is confirmed and a wash-out period is not needed for the subject, based on investigator's judgements the blood test required at V2 can be replaced by the data obtained 14 days before V2.
4. Serum lipids: total cholesterol, triglycerides, HDL-C, LDL-C, LDL/HDL ratio. Serum lipid results obtained 3 days prior to V1 is acceptable.
5. Doppler color flow mapping, and CT scan of the liver. CT scan will not be scheduled at visit 5 on subjects without fatty liver. Results of Doppler color flow mapping and CT scan of the liver obtained between V1 and V2 are acceptable.
6. hsCRP, IL-1, IL-6, and TNF-alpha.
7. WBC, RBC, Hb, Hct, RDW, platelet, MCV, MCH, MCHC, neutrophil-band and segment, lymphocyte, monocyte, eosinophil, and basophil.
8. Biochemical exam: AST, ALT, CPK, BUN and serum creatinine: visit 2 to visit 6; albumin, total bilirubin, direct bilirubin, ALP, total protein: V2, V5 and V6. At screening visit, serum creatinine shall be run for estimating glomerular filtration rate (GFR) and data obtained 3 days prior to V1 is acceptable.
9. Urinary exam: routine urine test (pH, protein, glucose, ketone, blood, urobilinogen, bilirubin, nitrite, leukocyte) and clinical microscopy.

#### **4.1.2 Schedule of Assessments**

##### **Screening activities:**

Before being enrolled to the study, patients should complete informed consent, review of medical history, physical examination, blood samples for lipid profile and biochemistry, demographic, anthropometric measures, urine pregnancy test, vital signs, and concomitant therapy record.

**Protocol: GHLIP-2-001**

**Study Sponsor: Golden Biotechnology Corporation**

**Every study visit day including Day 1, 29, 57, 85, 99:**

The patient who meets all the entry criteria are eligible for the study. During the study period, the patient have to undergo biochemistry assessment, vital signs measurements, anthropometric measures, physical examination, serum lipid test, concomitant therapy record, and adverse event assessment.

**Every study visit day including Day 1, 85, 99:**

During the study period, biomarker assessment, CBC and WBC differential, and urinary exam are conducted.

**Every study visit day including Day 1, 85:**

During the study period, electrocardiogram, baPWV, ABI, and image monitoring are performed.

**Every study visit day including Day 1, 29, 57, 85:**

Dispense new study drug pack to the patient (Day 1, 29, 57), collect unused portion of previous pack from the patient (Day 29, 57, 85), and ensure accountability information on patients' drug accountability log.

## **4.2 Selection of Population**

### **4.2.1 Inclusion Criteria**

1. Adults of either sex 20 to 75 years of age, inclusive, with a diagnosis of nonfamilial hypercholesterolemia or mixed hyperlipidemia as one of the following:
  - TG between 150 mg/dL and 500 mg/dL, and cholesterol between 160 mg/dL and 250 mg/dL
  - TG between 150 mg/dL and 500 mg/dL and LDL-C > 130 mg/dL).
2. Subject must be free of any clinically significant disease, other than nonfamilial hypercholesterolemia or mixed hyperlipidemia that would knowingly interfere with study evaluations.

**Protocol: GHLIP-2-001**

**Study Sponsor: Golden Biotechnology Corporation**

3. A wash-out period of 2 weeks will be applied to patients prior treated with lipid-lowering medication.
4. Subject must be willing to adhere to protocol requirements, and provide written informed consent.
5. Female of child-bearing potential must agree to use adequate contraception (hormonal or barrier method of birth control; abstinence) prior to study entry and for the duration of study participation.

#### **4.2.2 Exclusion Criteria**

1. Patients with secondary dyslipidemia caused by diabetes mellitus, hypothyroidism, obstructive liver disease, chronic renal failure or drugs which can increase LDL-C level (e.g. retinoids, cyclosporine A and phenothiazines) or decrease HDL-C level (e.g. progestins, androgens,  $\beta$ -blockers, probucol and anabolic steroid).
2. Patients with lifestyle that may interfere treatment efficacy, such as alcoholism or drinking habits more than 3 times per week, late dinner, late night supper, frequent oversea business traveler, frequent social gathering, and patients who cannot anticipate a diet control and lifestyle changes.
3. Patients with diabetes or history of coronary artery disease (has had myocardial infarction, cardiac intervention, cerebrovascular accident/stroke or transient ischemic attack less than 6 months prior to Visit 1).
4. Patients with hypertension that is uncontrolled defined as 2 consecutive measurements of sitting blood pressure of systolic  $>140$  mmHg or diastolic  $> 90$  mmHg at Visit 1.
5. Patient has a known hypersensitivity to Antroquinonol or related compounds.
6. Patient with uncontrolled intercurrent illness including, but not limited to, acute decompensated HF (exacerbation of chronic HF manifested by signs and symptoms that may require IV therapy), right heart failure due to severe pulmonary disease, diagnosed peripartum or chemotherapy induced cardiomyopathy within the 12 months prior to visit 1, or psychiatric illness/social situations that would limit compliance with study requirements.
7. Patients with a history of heart transplant or who are on a transplant list or with left ventricular assistance device (LVAD device).

**Protocol: GHLIP-2-001**

**Study Sponsor: Golden Biotechnology Corporation**

8. Patients with documented ventricular arrhythmia with syncopal episodes within the past 3 months prior to visit 1 that remained untreated.
9. Patients with confirmed severe primary pulmonary, renal (eGFR<30 ml/min/1.73 m^2) or hepatic (Child-Pugh B/C classification) disease.
10. Patients who can't stop current lipid lowering drug treatments based on investigator's judgement.
11. Patients with any malignancy, treated or untreated, within the past 5 years of Visit 1 whether or not there is evidence of local recurrence or metastases, with the exception of localized basal cell carcinoma of the skin or carcinoma in situ of the cervix.
12. Female patient during pregnancy, lactation or breastfeeding.
13. Patient has any other life-threatening complications.
14. Patient who is considered unreliable as to medication compliance or adherence to scheduled appointments, or inappropriate for inclusion determined by the investigators.
15. Any other reasons addressed by the investigators.

### **4.3 Randomization and Blinding**

According to the double-blind study design, enrolled patients are randomized in 1: 1: 1 :1 ratio to receive either Antroquinonol 150 mg, Antroquinonol 100 mg, Antroquinonol 50 mg, or placebo. The randomization sequence was generated using SAS version 9.3 with blocks of variable size and random seeds to ensure that allocation concealment is not violated through guessing of the allocation sequence at the end of each block. The aforementioned randomization code list was generated by the CRO and provided to Golden Biotechnology Corporation in order to pack and label the study drugs. Randomization data would not be accessible by anyone else involved in the study. The corresponding study group of individual subjects were recorded in a sealed envelope and were kept strictly confidential until the time of data lock. For this multi-center study, centralized randomization was applied. The investigator confirmed the subject

**Protocol: GHLIP-2-001**

**Study Sponsor: Golden Biotechnology Corporation**

fulfilled the inclusion and exclusion criteria and informed the randomization center. The sponsor's independent staff provided the randomization number in order. The study drugs labeled with randomization number was provided according to the request from each site. After enrollment, subjects were randomly assigned to receive one of the study treatments in a double-blind fashion. The identity of the treatments were concealed by the use of study drugs. The placebo was masked by the same appearance, odor and taste as the study drug (Antroquinonol), and used as well. Subjects, investigator, site staff, persons performing study assessments and data analysts remain blinded to the treatment assignment from the time of randomization until data lock.

## **5 SAMPLE SIZE DETERMINATION**

The sample size estimation of this study is using two-sample T-test under one-sided significance level 0.025, power 90%. Based on the Davidson's study, the TG reduction percentage change of 130 mg Fenoribrate from baseline to last visit was 36.6% for subjects who were treated with the study treatment, and the standard deviation was 2.4% and 5.3% for the study treatment and the control treatment. Assuming a drop-out rate of 20%, a sample size of 120 patients (30 patients per arm) were required to provide 96 evaluable patients (24 patients for each group) which indicates an achievement of 80% completion rate.

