9.2. Sample Size Considerations

The primary efficacy endpoint in this trial is “to compare the percentage change of triglyceride (TG) from baseline following a 12-week regimen of Antroquinonol versus placebo.” The objective of this trial is to assess the efficacy of the study treatment compared with control treatment. According to the literature review (FDA statistical reviews of Fibrate), the TG reduction percentage change of Fibrate from baseline to last visit was 36.6% for subjects who were treated with the study treatment, and 0.7% increased for the control treatment. According to prior published clinical reference, it is assumed that the mean TG percentage reduction is 27.5% and standard deviation is 40. The evaluable patient number should be at least 24 patients for each group under one-sided significance level 0.025 and power 90%. Considering a 20% drop-out rate, a sample size of 30 patients should be enrolled to each group, and a total of 120 patients will be recruited into this study. The sample size calculation was derived using PASS 2008.

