## **7.7 Adjustments for Multiplicity**

For comparison of percentage change in TG of three groups with placebo, 100mg vs. 50 mg, and 150mg vs. 100mg, the post hoc tests will be used to detect which group differ from the rest while statistical significance of ANCOVA or Kruskal-Wallis test. For ANCOVA, the required significance criterion alpha is 0.05 divided by the total number of tests. To correct the multiple testing for primary endpoint, the p-value will be adjusted according to Bonferroni's method to reject the null hypothesis (p-value <0.05/m, m= number of tests). In addition, two independent t-test will also be used for pairwise comparison (p-value=0.05 for all multiple tests). For Kruskal-Wallis test, two independent t-test or Wilcoxon rank-sum test will be used for pairwise comparison (p-value=0.05 for all multiple tests).

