## 9.7 Interpretation and Conclusion

All tests are two-tailed unless otherwise specified and the overall significant level is set to be 0.05. When the number of hypothesis in a test is increased, the Bonferroni correction would be used to test each of the individual tests at a significance level of  $0.05/m$  ( $m$ = number of tests=5, section 9.3). Statistical significance will be demonstrated if the p-value is less than the significance level of test. Regardless of the outcome declared statistically significant, all results could be stated on the Clinical Study Report (CSR).

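### The stated 90% power matches only the unadjusted pairwise tests, not the 0.05/5 Bonferroni rule by which SAP 9.7 declares significance

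*SAP*

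**What the plan says.** **Sample size.** Protocol 9.2 states: "The evaluable patient number should be at least 24 patients for each group under one-sided significance level 0.025 and power 90" per cent. On the inputs, "it is assumed that the mean TG percentage reduction is 27.5% and standard deviation is 40". The same section cites fibrate data: "the TG reduction percentage change of Fibrate from baseline to last visit was 36.6" per cent, "and 0.7% increased for the control treatment". SAP 5 repeats the level and power ("using two-sample T-test under one-sided significance level 0.025, power 90" per cent). It cites the same 36.6% reduction but gives different variability: "the standard deviation was 2.4% and 5.3% for the study treatment and the control treatment". Neither section mentions multiple comparisons.

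**Bonferroni rule.** SAP 7.7: "For ANCOVA, the required significance criterion alpha is 0.05 divided by the total number of tests". SAP 9.7, which defines when significance is demonstrated, says that "the Bonferroni correction would be used to test each of the individual tests at a significance level of" 0.05/m, with m = 5 referring to SAP 9.3. It makes tests two-tailed unless otherwise specified, with an overall level of 0.05, and does not limit the rule to the ANCOVA path.

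**Unadjusted rule.** SAP 7.7 adds independent t-tests at 0.05 for the same comparisons, and SAP 9.3 lists these beside Bonferroni's method after a significant ANCOVA. If normality fails, Kruskal-Wallis replaces ANCOVA. Section 7.7 then sets the pairwise t or Wilcoxon rank-sum tests at 0.05 with no correction.

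**Order.** On both paths the five pairwise comparisons (three doses against placebo, 100 against 50 mg, 150 against 100 mg) follow an omnibus test significant at 0.05.

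**The concern.** The power is stated at one-sided 0.025, which has the same critical value as two-sided 0.05 in the direction of benefit. The section that defines significance uses a two-sided level five times smaller. A dose with a two-sided p-value between 0.01 and 0.05 passes the unadjusted t-test and fails the Bonferroni rule, and the SAP does not say which result counts.

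Two things are at stake. The dose claim is open to choice after the results are seen. And a dose that misses 0.01 would be reported from a trial described as having 90% power, which makes the negative result look firmer than it is.

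**Working it through.** **Inputs.** n = 24 evaluable per arm; one-sided 0.025; power 90%; difference 27.5 and SD 40 (all Protocol 9.2). Literature difference 36.6 + 0.7 = 37.3 (Protocol 9.2). Decision level 0.05/5 = 0.01 two-sided, or 0.005 in the direction of benefit (SAP 9.7).

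**Formula.** Two-sample t-test: d = difference/SD, noncentrality = d × √(n/2) = d × √12 = 3.464d, and power = P(noncentral t > critical t). With two arms df = 46, and the critical values are 2.013 (one-sided 0.025) and 2.687 (one-sided 0.005). With the error pooled over four arms and one covariate df = 91, and the value for 0.005 is 2.631. The df = 91 column changes only the degrees of freedom; it credits no variance reduction from the covariate.

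**Step 1: the plan's own figure.** For 27.5/40, d = 0.6875 and the noncentrality is 2.382. Power with 24 per arm at one-sided 0.025 is 64.5%, and 90% needs 46 per arm (45 by normal approximation). So 24 is not reproduced. The nearest two-sample reading is 37.3 with SD 40 (d = 0.9325, noncentrality 3.230): 88.5% with 24 per arm, 26 per arm for 90%. A one-sample formula with 27.5/40 gives 25. The SAP's SDs of 2.4 and 5.3 (root mean square 4.11) would need only 1 to 3 per arm. The dropout step does reproduce: 24/0.8 = 30 per arm, 120 in total.

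**Step 2: power at each level, 24 per arm, no covariate.**

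| Assumption | One-sided 0.025 (df 46) | Two-sided 0.01 (df 46) | Two-sided 0.01 (df 91) | n per arm for 90% at 0.01 |
|---|---|---|---|---|
| 27.5, SD 40 (d = 0.6875) | 64.5% | 39.0% | 40.6% | 65 |
| 37.3, SD 40 (d = 0.9325) | 88.5% | 70.5% | 72.4% | 36 |
| d = 0.956, solved so that 24 per arm gives 90% | 90% | 73.1% | 75.0% | 35 |

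The last row isolates the change of level. It is a device, not a reading of the documents' inputs.

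**Step 3: the level alone.** By normal approximation, n is multiplied by [(2.576 + 1.282)/(1.960 + 1.282)]² = 1.42, so 24 becomes about 34 whatever the effect and SD.

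**Step 4: the omnibus gate.** A simulation (20,000 runs, four-arm ANOVA at 0.05 first, no covariate) gives the chance that one given dose passes both the gate and its t-test against placebo. For 27.5/40 this is about 55% at unadjusted 0.05 and 37-39% at 0.01. For 37.3/40 it is about 85% and 70%. The gate costs more at the unadjusted level than at 0.01.

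**The case against.** A reader might infer that the trial was sized for a test it does not use. The documents do not support that. SAP 7.7 and 9.3 plan independent t-tests at unadjusted 0.05, with the same critical value in the direction of benefit as the sizing test, and the Kruskal-Wallis path in 7.7 uses 0.05 alone. What stands is narrower: two unreconciled pairwise rules, with the stated power fitting only one. Nor can the unadjusted rule simply be taken as decisive, since the Bonferroni text in SAP 7.7 and 9.7 would then have no function.

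A reader might also take 73-75% as the correct replacement for 90%. It is not, because it presupposes the 90% that 27.5 and 40 fail to give.

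Three further objections carry some weight.

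- **The primary hypothesis in SAP 9.1 is the four-group omnibus test, and the objective concerns Antroquinonol rather than each dose.** If all doses work equally, the chance that at least one succeeds at 0.01 after the gate is about 92% (d = 0.956) or 63% (27.5/40). If only one dose works it is about 75% at d = 0.956. But both documents state power for a two-group comparison, so that is the figure to correct.
- **The planned model is ANCOVA, not a t-test.** If SD 40 is unadjusted, a baseline correlation of 0.3 to 0.6 (an assumption; the documents give none) divides it by a factor √(1 − r²) smaller than 1. Power at 0.01 then becomes about 45-64% for 27.5, 77-92% for 37.3, and 80-93% for d = 0.956. A strong covariate could therefore restore 90% under the larger effects. The plan makes no such argument and does not say whether its SD is adjusted.
- **The larger arithmetic fault is 24 against 45-46 per arm.** That is true and needs its own repair, but correcting the effect or SD would leave the level mismatch in place.

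**Conclusion.** The concern holds as an internal inconsistency. The 90% in Protocol 9.2 and SAP 5 relates to one two-sample test at one-sided 0.025. It does not describe power under the 0.05/5 rule in SAP 9.7, and the SAP leaves open which of its two pairwise rules decides a dose claim.

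Without a covariate gain and with 24 evaluable per arm, power per dose-placebo comparison at two-sided 0.01 runs from about 39-41% to 70-72% as the difference goes from 27.5 to 37.3 with SD 40. The figures assume normal data and equal SDs. They apply to one dose against placebo, not to success of any dose, and cannot be narrowed until the effect and SD are reconciled.

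**What to change.** Keep 120 patients.

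1. In SAP 7.7, 9.3 and 9.7, state that the Bonferroni-adjusted comparison (0.05/5, two-sided) decides the dose-versus-placebo claims on both the ANCOVA and Kruskal-Wallis paths. Label the unadjusted 0.05 tests as supportive.
2. In Protocol 9.2 and SAP 5, replace the 90% with the power per dose-placebo comparison at that level. Compute it from one reconciled effect and SD (Protocol 9.2 has 27.5 and 40; SAP 5 has 36.6 with SDs 2.4 and 5.3). Say whether the figure allows for the baseline covariate and for the omnibus gate. If a different multiplicity rule is chosen, recompute at its level.

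The cost is wording in five sections and one recalculation, with no added patients. It should be done before the SAP is approved, since SAP 6.2 bars database lock and unblinding until then. The downsides are a less favourable stated power, and that a dose with p between 0.01 and 0.05 could be reported only as supportive.
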